## 10.1.2 List of Statistical Figures

Figure	Figure Title
14.2	Efficacy
14.2.1.1	Kaplan-Meier Plot of Time to Onset of Symptom Relief for Composite Investigator-Assessed Symptom Scores for Icatibant Exposure Number 1 (Efficacy Population)
14.2.1.2	Kaplan-Meier Plot of Time to Onset of Symptom Relief for Composite Investigator-Assessed Symptom Scores by Icatibant Exposure Number for Icatibant Exposure Number 2 and 3 (Efficacy Population)
14.2.2.1	Kaplan-Meier Plot of Time to Minimum Symptoms for Composite Investigator-Assessed Symptom Scores for Icatibant Exposure Number 1 (Efficacy Population)
14.2.2.2	Kaplan-Meier Plot of Time to Minimum Symptoms for Composite Investigator-Assessed Symptom Scores by Icatibant Exposure Number for Icatibant Exposure 2 and 3 (Efficacy Population)
14.2.3.1	Mean Composite Investigator-Assessed Symptom Score over Time for Icatibant Exposure Number 1 (Efficacy Population)
14.2.3.2	Mean Composite Investigator-Assessed Symptom Score over Time by Icatibant Exposure Number for Icatibant Exposure Number 2 and 3 (Efficacy Population)
14.2.4.1	Kaplan-Meier Plot of Time to Onset of Symptom Relief for FPS-R Scores for Icatibant Exposure Number 1 (Subjects from Efficacy Population with FPS-R data)
14.2.4.2	Kaplan-Meier Plot of Time to Onset of Symptom Relief for FPS-R Scores by Icatibant Exposure Number for Icatibant Exposure Number 2 and 3 (Subjects from Efficacy Population with FPS-R data)
14.2.5.1	Kaplan-Meier Plot of Time to Onset of Symptom Relief for FLACC Scores for Icatibant Exposure Number 1 (Subjects from Efficacy Population with FLACC data)
14.2.6.1	Kaplan-Meier Plot of Time to Initial Symptom Relief for Icatibant Exposure Number 1 (Efficacy Population)
14.2.6.2	Kaplan-Meier Plot of Time to Initial Symptom Relief by Icatibant Exposure Number for Icatibant Exposure Number 2 and 3 (Efficacy Population)

## 10.1.3 List of Data Listings

Listings	Data Listing Heading
16.2.1.1	Subject Disposition – Safety Population
16.2.1.2	Inclusion/Exclusion Criteria - All Population
16.2.2	Protocol Deviations – All Subjects
16.2.4.1	Demographic and Pre-treatment Characteristics - Safety Population
16.2.4.2.1	Medical History – Safety Population
16.2.4.2.2	HAE History – Safety Population
16.2.4.3.1	Concomitant Medications Other than Rescue Medication – Efficacy Population
16.2.4.3.2	Concomitant Medications Other than Rescue Medication - Safety Population
16.2.4.4.1	Rescue Medication - Efficacy Population
16.2.4.4.2	Rescue Medication - Safety Population
16.2.4.5	Details of Attack – Efficacy Population
16.2.5	Study Drug Administration – Safety Population
16.2.6.1	Symptom Score Assessed by Investigator – Efficacy Population
16.2.6.2	FLACC – Efficacy Population
16.2.6.3	FPS-R – Efficacy Population
16.2.6.4	Initial Symptom Relief Assessed by Investigator - Efficacy Population
16.2.7.1	Pre-Treatment Adverse Events - Safety Population
16.2.7.2	Treatment-Emergent Adverse Events - Safety Population
16.2.7.3	Treatment-Emergent Serious Adverse Events - Safety Population
16.2.7.4	Treatment-emergent Adverse Events Resulted in Study Discontinuation – Safety Population
16.2.7.5	Serious Adverse Events – All Subjects
16.2.7.6	Local Tolerability Assessed by Investigator – Safety Population
16.2.8.2.1	Clinical Laboratory Evaluations – Hematology - Safety Population
16.2.8.2.2	Abnormal Laboratory Values – Hematology - Safety Population
16.2.8.3.1	Clinical Laboratory Evaluations – Chemistry - Safety Population
16.2.8.3.2	Abnormal Laboratory Values – Chemistry - Safety Population
16.2.8.4.1	Clinical Laboratory Evaluations – Urinalysis - Safety Population
16.2.8.4.2	Abnormal Laboratory Values – Urinalysis - Safety Population
16.2.8.5.1	Reproductive Hormone Assessments - Safety Population
16.2.8.5.2	Reproductive Hormone Assessments deemed Abnormal - Safety Population
16.2.8.6	Urine Pregnancy Test (Females Only) - Safety Population
16.2.8.7	Immunogenicity - Safety Population
16.2.8.8.1	Electrocardiogram Data- Safety Population
16.2.8.8.2	Abnormal Electrocardiogram Data - Safety Population
16.2.8.9	Vital Signs - Safety Population
16.2.8.10	Menstrual Cycle History (Pubertal/Post-pubertal Females Only) - Safety Population

## 10.2 APPENDIX II: Definitions and Programming Conventions

### 10.2.1 Age Calculation

Age will be calculated as the date of study drug administration minus the date of birth and displayed rounded to one decimal place.

If the date of birth is not complete (i.e., contains only partial information such as month and year or only year), then the non-missing date parts will be used to calculate the subject's age. If the date of birth is completely missing, then the age reported in the clinical database will be used as the subject's age.

### 10.2.2 BMI Calculation

BMI will be calculated using the standard formula (below) and displayed rounded to one decimal place.

$$\text{BMI (kg/m}^2\text{)} = (\text{body weight in kilograms}) / (\text{height in meters})^2$$

### 10.2.3 Weight and Height Percentile Calculation

Weight and height will be converted to percentiles using CDC growth charts based on the subject's sex and age.

### 10.2.4 Time-to-Event Endpoints

Time-to-event endpoints will be calculated from the time of study drug administration to the earliest time point at which endpoint is achieved. The actual study drug administration date and time, and the first assessment date and time at which at the endpoint criteria is satisfied will be used for this calculation.

### 10.2.5 Study Day of an Event

Study day is calculated as the date of event of interest – date of treatment + 1 for dates on or after treatment, and date of event of interest – date of treatment for dates prior to treatment.

### 10.2.6 Duration of an Event

The duration of an event is calculated as the event stop date/time – event start date/time if time is not missing, and event stop date – event start date + 1 if either the start or stop time is missing.

### 10.2.7 Attribution of Concomitant Medications

For subjects treated with study drug for more than once during the study, concomitant medications will be programmatically assigned to the appropriate attack(s) by comparing the reported dates and times of study drug administration for all exposures with that of start and

end dates and times of concomitant medication. Medications will be assigned to the study drug administration(s) for which the concomitant medication was administered during the 5-day interval after the study drug administration.

If the concomitant medication start time is missing, but the concomitant medication start date is the same as a dosing date, then the concomitant medication will be attributed to the attack that was dosed on that day.

#### 10.2.8 Calculating Years since Diagnosis and Months since Last Attack with Partial Dates

For the calculation of durations using dates with a missing day component, but non-missing month and year components, the date will be assumed to occur at the first of the month. For the calculation of durations using dates with missing day and month components, but a non-missing year component, the date will be assumed to occur at the first of the year. If the year component is missing the duration will be missing.

#### 10.2.9 Handling of Missing Individual Symptom Assessment at Baseline

If an individual symptom assessment was missing at baseline before an on-study icatibant exposure, then the missing symptom assessment will be considered as the mean of other individual symptom severity in the calculation of the composite symptom severity at baseline.

#### 10.2.10 Deriving Time to First Use of Rescue Medication for Subjects with Missing Time to Onset of Symptom Relief

Subjects with missing pretreatment symptom assessments would be excluded from the time to onset of symptom relief analysis. If a subject was excluded from the time to onset of symptom relief analysis, but received a rescue medication within 48+4 hours after an on-study icatibant exposure, then the time between the icatibant treatment and the first rescue treatment use would be considered as time to first use of rescue medication.

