8.4.2 Treatment Period (Day 1 to Day 8 [± 1 Day])

8.4.2.1 Day of Subsequent Attack (Day 1)

When a pubertal/postpubertal subject experiences an acute HAE attack, subjects (parent/legal guardian/caregiver) will contact the hospital/study center (or their home healthcare professional in the event the investigator is not available) to confirm the HAE attack diagnosis.

The investigator (or the home healthcare professional in the event the investigator is not available), in consultation with the subject's preference, will determine whether the subject will be treated at the hospital/study center, at home by a qualified home healthcare personnel, at home by the trained parent/legal guardian/caregiver, or by self-administration. The qualified home healthcare person will be contacted, if applicable.

The following will occur prior to study drug administration:

	Subject Treated at Study Site	Subject Treated at Home
Call hospital/study center (or their home healthcare professional in the event the investigator is not available) to confirm the HAE attack diagnosis	X	X
Investigator Symptom Score	X	
Home Healthcare Provide or Parent/Legal Guardian/Caregiver Symptom Score	X	X
Subject Self-Assessment of Pain	X	X
Urine pregnancy test	X	X
Concomitant Medications	X	X
Adverse Events	X	X

- Assessment of HAE symptoms
 - The investigator will assess HAE symptoms using the Investigator Symptom Score if the subject is treated at the hospital/study center
 - The home healthcare provider will assess HAE symptoms using the Home Healthcare Provider or Parent/Legal Guardian/Caregiver Symptom Score if the subject is treated at home
 - The parent/legal guardian/caregiver will assess HAE symptoms using the Home Healthcare Provider or Parent/Legal Guardian/Caregiver Symptom Score if the subject is treated at either the hospital/study site or at home
- Subject will self-assess HAE-related pain using diary FPS-R
- Urine pregnancy test for females of child-bearing potential
- Concomitant medications will be recorded
- Adverse events will be recorded

Once the pretreatment assessments are completed, icatibant will be administered (Day 1, Time 0).

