#### 7.8.1 Investigator Symptom Score

The primary efficacy endpoint is the time to onset of symptom relief measured using the investigator-reported symptom score. Eight symptoms will be assessed for abdominal and cutaneous attacks, and 13 symptoms will be assessed for laryngeal attacks. Time to onset of symptom relief is defined as the duration of time in hours from study drug administration to the earliest time post-treatment at which there is at least a 20% improvement in the composite (or average) post-treatment symptom score with no worsening of any single component score.

Subjects not achieving the onset of symptom relief will be censored at the time of their last symptom assessment. Time to onset of symptom relief will be summarized using the Kaplan-Meier method.

An alternative efficacy endpoint is the time to minimum symptoms measured using the investigator-reported symptom score. It is defined as the earliest time post-treatment when all symptoms are either mild or absent. Subjects not achieving the minimum symptom criteria will be censored at the time of their last symptom assessment. Time to minimum symptoms will be summarized using the Kaplan-Meier method. Subjects with all symptoms as mild or absent at pretreatment will be excluded from this analysis.

The composite investigator-reported symptom score and the change from pre-treatment in the composite investigator-reported symptom score will be summarized by study time-point. Furthermore, the symptom scores associated with individual symptoms will be summarized by study time-point. The mean composite investigator-assessed symptom score will be plotted by study time-point by pubertal status stratification group.

For individual investigator-reported symptom scores, a shift table from baseline will be presented for each post-treatment time point. The analysis will be repeated to assess shift in the individual symptom scores from the 2 hour time-point.

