### 7.8.4 Other Efficacy Analyses

#### Time to First Use of Rescue Medication

The number and percentage of subjects who received rescue medications before the onset of symptom relief will be summarized. Time to first use of rescue medication prior to onset of symptom relief will be calculated from the time of study drug administration to the first use of rescue medication prior to the onset of symptom relief. Subjects not using rescue medication prior to the onset of symptom relief will be censored at the time of their onset of symptom relief. Time to first use of rescue medication will be summarized using the Kaplan-Meier method. This analysis will only be performed if there are at least 5 subjects for a given attack who used rescue medication prior to attaining symptom relief.

Subjects who received rescue medication before the onset of symptom relief will be denoted in the listing on rescue medication for the efficacy population.

Analyses on time to first use of rescue medication will be performed for the initial icatibant exposure and both subsequent icatibant exposures.

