g For subjects treated at the hospital/study center only.

- h The subject will be observed for a minimum of 2 hours after icatibant administration. If after the completion of the assessments scheduled for 2 hours post-treatment, the subject's symptoms are absent or mild, no further Day 1 assessments are required. If the subject's symptoms at 2 hours post-treatment are moderate, severe, or very severe, the subject will be assessed every 2 hours until the subject's symptoms are absent or mild.
- i Injection site reaction will be recorded (1 hour [ $\pm 10$  minutes] post dose and 2 [ $\pm 0.5$ ] hours post dose, and every 2 [ $\pm 0.5$ ] hours until injection site reaction is mild or absent (if the subject's injection site reaction is not mild or absent at 2 hours post dose)

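### SAP 10.2.10 admits subjects without a relief time to the time-to-first-rescue analysis only if they were rescued, so the Kaplan-Meier estimate is biased upward when that analysis is run

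*SAP*

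**What the plan says.** **Relief.** SAP 7.8.1: "The primary efficacy endpoint is the time to onset of symptom relief measured using the investigator-reported symptom score".

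**Time to first rescue.** SAP 7.8.4 counts rescue given before onset of relief and applies to the initial and both subsequent exposures. It has one censoring rule: "Subjects not using rescue medication prior to the onset of symptom relief will be censored at the time of their onset of symptom relief". It also has a gate, tied to rescue before relief: "This analysis will only be performed if there are at least 5 subjects for a given attack who used rescue medication prior to attaining symptom".

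**When no relief time exists.** SAP 10.2.10 first says: "Subjects with missing pretreatment symptom assessments would be excluded from the time to onset of symptom relief analysis". It continues: "If a subject was excluded from the time to onset of symptom relief analysis, but received a rescue medication within 48+4 hours" of dosing. The consequence for that subject is: "then the time between the icatibant treatment and the first rescue treatment use would be considered as time to first use of rescue medication". There is no counterpart for an excluded subject who was not rescued.

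**Who has an investigator score.** Protocol 8.4.2.1, on subsequent attacks: "The investigator will assess HAE symptoms using the Investigator Symptom Score if the subject is treated at the hospital/study center". Footnote g to the investigator row in SAP 10.3.3 reads: "For subjects treated at the hospital/study center only". Home-treated attacks are scored on the same five-point scale by a home healthcare provider or caregiver (Protocol 7.11.1.2). Protocol 10.7 plans averages, changes from baseline and shift tables for those scores. SAP 7.8 names only the investigator score, FPS-R and FLACC, and the SAP's list of outputs has no caregiver-score table.

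**Display.** SAP 7.2 and 7.8 split exposures 2 and 3 into HCP and Caregiver Administration; the second includes home healthcare providers, patients and parents.

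**The concern.** Whether an excluded subject enters the analysis is decided by the outcome being analysed. With rescue, the subject is an event. Without rescue, the subject has no analysis time. A dataset programmed literally from this text gains events without the matching censored subjects.

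The two groups also do not share an event. A scored subject rescued after relief is not an event, while an unscored subject rescued at any time up to 52 h is. Protocol 10.8 contains only the rescue-before-relief definition, yet SAP 8.2 declares no change from the protocol's analyses.

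At the initial exposure, given at the hospital or study center, this touches only the occasional subject whose pretreatment assessment was missed. At exposures 2 and 3 it may cover a whole category of attacks, and that category falls mainly in one of the two displayed columns.

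**Working it through.** The documents give no figure to reproduce: the sample size is empirical (SAP 4.5), and no rescue rate or number of home-treated attacks is stated. The check traces the rules and then applies them to assumed counts.

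**Step 1: does a home-treated attack fall under 10.2.10?**
- Relief uses the investigator score (SAP 7.8.1).
- That score is taken only for site-treated subjects (Protocol 7.11.1.1 and 8.4.2.1; SAP 10.3.3, footnote g).
- Imputation of pretreatment items requires that the assessment was performed (SAP 9.2.1), so it cannot supply a score that was never taken.
- The SAP does not say that caregiver scores replace investigator scores.

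On the written rules the answer is yes. It becomes no if caregiver scores are substituted.

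**Step 2: crude share among attacks that have an analysis time.** Let n be attacks and r rescued attacks, by place of treatment.
- As written: (r_site + r_home) / (n_site + r_home)
- All attacks kept: (r_site + r_home) / (n_site + n_home)

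Assumed splits, each with 5 rescued, the smallest number at which the analysis runs. N = 10 is the protocol's minimum number of adolescents treated three times; N = 20 is the planned number of pubertal/postpubertal subjects.

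| N | Home-treated | Rescued, site + home | As written | All kept |
|---|---|---|---|---|
| 10 | 5 | 2 + 3 | 5/8 = 62.5% | 5/10 = 50% |
| 10 | 8 | 1 + 4 | 5/6 = 83% | 5/10 = 50% |
| 20 | 10 | 2 + 3 | 5/13 = 38.5% | 5/20 = 25% |

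**Step 3: Kaplan-Meier cumulative rescue by 10 h.** Assume site rescues at 0.5 and 0.8 h, the remaining site subjects censored at relief at 1 h, and home rescues at 3, 6 and 10 h.
- N = 10, 5 home-treated, as written: 1 − (7/8)(6/7)(2/3)(1/2)(0/1) = 100%.
- The same, with the 2 rescue-free home attacks censored at 48 + 4 = 52 h: 1 − (9/10)(8/9)(4/5)(3/4)(2/3) = 68%.
- N = 20, 10 home-treated, as written: 1 − (12/13)(11/12)(2/3)(1/2)(0/1) = 100%.
- The same, with the 7 rescue-free home attacks censored at 52 h: 1 − (19/20)(18/19)(9/10)(8/9)(7/8) = 37%.
- Home-treated attacks alone, N = 10: 100% as written, against 1 − (4/5)(3/4)(2/3) = 60%.

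The 68% exceeds the crude 50% because site subjects leave the risk set at relief, long before the home rescues. Pooling the two censoring schemes is therefore not a clean repair either.

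**Step 4: how often would the gate be met?** Exact binomial probability of at least 5 rescued:
- N = 10: 3% at a true rescue rate of 20%, 15% at 30%, 62% at 50%.
- N = 20: 4% at 10%, 37% at 20%, 76% at 30%.

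The SAP does not say whether rescued subjects without a relief time count towards the five. The examples assume that they do.

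**The case against.** **The gate.** Unless rescue is common, no Kaplan-Meier result will exist at exposures 2 and 3. This stands and limits how often the flaw can show.

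**Rescue incidence is reported by another route.** SAP 7.9.10 summarises rescue within 48+4 h by exposure number for both populations (Tables 14.1.4.1 to 14.1.4.6), with no need for a symptom score. This stands, and it makes crude incidence largely recoverable. It does not correct the time-to-event output.

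**A stronger reading.** A reader might infer that the report will show 100% rescue incidence for home treatment after only one or two rescues, and so a false signal against home treatment. The documents do not support that. One or two rescues do not meet the gate. SAP 10.2.10 derives a time and does not say that unrescued subjects leave the count and percentage in 7.8.4. SAP 7.2 bases efficacy analyses on the Efficacy Population. What can be said is that the denominator of that percentage is not stated.

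**Caregiver scores.** Home-treated attacks do have a pretreatment symptom score, 10.2.10 does not specify an investigator score, and a planned Caregiver Administration column for relief makes little sense if every home attack is excluded. The sponsor may therefore intend substitution. That is a fair reading of intent, but the SAP does not say it. If it is intended, the problem shrinks to attacks with no pretreatment score at all.

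**Conclusion.** The flaw is real, and it is minor. As written, SAP 10.2.10 makes entry into the time-to-first-rescue analysis depend on being rescued and changes the event for those admitted. When the gate is met, the Kaplan-Meier estimate is biased upward, most in the Caregiver Administration column. In the assumed splits shown, the rescued share is 38.5% to 83% as written, against 25% to 50% with all attacks kept. Below the gate no Kaplan-Meier result is affected.

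This rests on four assumptions:
- Excluded subjects without rescue drop out of the Kaplan-Meier analysis because they have no time.
- Onset of relief in 7.8.4 and 10.2.10 means the investigator-score endpoint.
- Caregiver scores are not substituted at home.
- Caregiver Administration roughly matches home treatment, although the SAP defines it by who gives the drug and not by place.

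The direction of the bias does not depend on the assumed counts; its size does. Rescue use is a secondary endpoint in a descriptive study without hypothesis tests, so no main conclusion turns on it.

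**What to change.** Rewrite SAP 10.2.10 so that attacks without an evaluable relief time are handled the same way whether or not rescue was given. Either option works:

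1. Restrict the rescue-before-relief analysis to attacks with an evaluable relief time, and report rescue within 52 h as n/N of all treated attacks in a separate row.
2. Keep all attacks without a relief time in a separate rescue-within-52-h analysis, with the rescue-free ones censored at 52 h. Do not pool them with subjects censored at relief.

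Also state:
- that the percentage in 7.8.4 uses all treated attacks at that exposure;
- whether rescued subjects without a relief time count towards the five;
- whether caregiver scores define relief for home-treated attacks.

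Record the resulting rule in SAP 8.2 if it departs from Protocol 10.8.

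The cost is SAP wording and a small programming change. No new data are needed: concomitant medications are already recorded on Days 1, 2 and 8 of subsequent attacks (Protocol 8.4.2 and 8.4.3.1), so rescue-free status through 52 h can be derived.

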#### 10.2.11 Attribution of AEs

For subjects treated with study drug for more than one attack during the study, adverse events will be programmatically assigned to the appropriate attack by comparing the reported dates and times of first study drug administration for all attacks with that of AE onset. Events will be assigned to the latest attack for which the study drug administration preceded the AE onset. If the adverse event start time is missing, but the adverse event start date is the same as a dosing date, then the adverse event will be attributed to the attack that was dosed on that day.

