4.1.3.2 Subsequent Icatibant-Treated Attacks

Subsequent treatment with icatibant may be offered to pubertal/postpubertal subjects who have received initial treatment and who present subsequently with an attack at least 3 days after prior treatment. Subjects will be eligible for treatment with icatibant until a total number of at least 10 adolescents have been treated 3 times with icatibant.

For all subjects who remain enrolled in the study for longer than 6 months, a study visit will be scheduled every 6 months to collect baseline information and to conduct training for parents/legal guardian/caretakers for subjects who have expressed an interest in receiving icatibant at home. In addition, for all subjects who remain enrolled in the study a safety telephone contact will be scheduled every month to collect information concerning AEs, weight, eligibility, and HAE attacks not treated within the study.

When a pubertal/postpubertal subject experiences an acute HAE attack, subjects (parent/legal guardian/caregiver) will contact the hospital/study center (or their home healthcare professional in the event the investigator is not available) to confirm the HAE attack diagnosis.

The investigator (or the home healthcare professional in the event the investigator is not available), in consultation with the subject's preference, will determine whether the subject will be treated at the hospital/study center, at home by a qualified home healthcare personnel, or at home by the trained parent/legal guardian/caregiver. The qualified home healthcare person will be contacted, if applicable.

For subsequent attacks, study drug may be administered by study site personnel at the hospital/study center or by qualified home healthcare personnel at the subject's home. Alternatively, a parent/legal guardian/caregiver will be allowed to administer or the subject (under the supervision of a parent/legal guardian/caregiver) will be allowed to self-administer the investigational product after having received appropriate training. For all subsequent laryngeal attacks, subjects should be advised to seek medical attention in an appropriate healthcare facility immediately following treatment with icatibant.

Except for PK determinations, all primary and secondary endpoints are to be measured after each administration. Safety, reproductive hormones, and other assessments in association with

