7.16 Recording of Adverse Events

Adverse events will be collected over an observation period from the time of treatment until the final follow-up visit 90 (± 7) days after investigational product administration (or until the event has resolved/stabilized or an outcome is reached, whichever comes first). Adverse event monitoring and the period of observation defined for this study are described in Section 7.17.4.1.

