#### 7.9.1 Adverse Events

Adverse events (AE) will be collected over an observation period from the time of treatment until the follow-up visit 90 ( $\pm 7$ ) days after investigational product administration (or until the event has resolved/stabilized or an outcome is reached, whichever comes first). Any serious adverse events (SAE), regardless of relationship to investigational product, which occurs in a subject after informed consent, should be recorded by the clinical site on a serious adverse event form.

AEs will be coded using MedDRA Version 16.0. A summary of subjects with treatment-emergent adverse events defined as AEs which occurred or worsened on or after the time of the first study drug administration will be presented. The summary will include the number and percentage of subjects who experience any AEs, any related AE, any severe AE, any related severe AE, any SAE, any related SAE, and any injection site reaction which was deemed an SAE; as well as the number of events in each category. Additionally, the summary table will include the number and percentage of subjects with AEs result in death.

Related AEs are AEs assessed as possibly, probably, or definitely related to the study treatment.

Treatment emergent AEs will be summarized by system organ class (SOC) and preferred term by pubertal status stratification level and icatibant exposure number. Tabulations will be presented sorted by SOC in alphabetical order and by PT within each SOC by descending frequency. The number and percentage of subjects experiencing an AE, as well as total number of AEs, will be tabulated. Treatment emergent AEs by SOC and preferred term also will be tabulated by severity and by relationship to treatment. In the case of multiple occurrences of the same AEs (at the preferred term level) in an individual subject, the AE that is classified as the most severe (i.e., maximum severity) will be identified for the analysis by severity and the AE that has the closest relationship to study drug will be identified for the analysis by relationship. Treatment emergent SAEs will be tabulated according to SOC and preferred term and provided in a data listing.

For analyses on treatment emergent AEs, in addition to summaries by icatibant exposure number, the analyses on all treatment emergent AEs by pubertal status stratification level and overall will be performed as well.

Pre-treatment AEs will be presented in a listing.

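### The rule assigning adverse events to doses has no time limit, so by-exposure percentages mix unequal follow-up and no person-time is shown

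*SAP*

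**What the plan says.** **Attribution.** SAP 10.2.11, for subjects dosed more than once: "Events will be assigned to the latest attack for which the study drug administration preceded the AE onset".

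**Treatment-emergent.** SAP 7.9.1 counts "treatment-emergent adverse events defined as AEs which occurred or worsened on or after the time of the first study drug administration". This fixes a start and no end.

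**Collection period.** The documents differ.
- SAP 7.9.1: "Adverse events (AE) will be collected over an observation period from the time of treatment until the follow-up visit 90" (±7) days after administration.
- Protocol 7.16: "Adverse events will be collected over an observation period from the time of treatment until the final follow-up visit 90" (±7) days after administration. The word final lets the period span the gaps between doses.
- Protocol 4.1.3.2, for all subjects who remain enrolled: "a safety telephone contact will be scheduled every month to collect information concerning AEs". Appendix 3 marks AEs at the repeat baseline visit and at every month after it.

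**Spacing of doses.** Re-treatment is open to pubertal/postpubertal subjects "who present subsequently with an attack at least 3 days after prior treatment" (Protocol 4.1.3.2). Protocol 4.3 says the inactive periods between doses vary in length and gives no maximum. Visits recur every 6 months for subjects enrolled longer than that.

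**Output.** SAP 7.9.1 tabulates the number and percentage of subjects with an AE, and the number of AEs, by exposure number. Exposure 1 is split by pubertal status; exposures 2 and 3 are split by who administered the dose. No subject-time or follow-up summary per exposure is listed. A separate summary covers all treatment-emergent AEs (TEAEs) by pubertal status and overall.

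**The concern.** Continued safety after repeated exposures is a stated objective (Protocol 2.2, SAP 3.2), and Protocol 10.6 bases the safety assessment mainly on the frequency of TEAEs. A reader will naturally look across the exposure 1, 2 and 3 tables for a change with repeated dosing, and across the prepubertal and pubertal/postpubertal columns of exposure 1.

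A percentage of subjects with at least one event rises with time observed, whatever the drug does. If one exposure's events accumulate over many months and another's stop near Day 97, the percentages differ for that reason alone. The direction cannot be predicted from the documents. Where long gaps predominate, earlier exposures look worse and a real increase at dose 3 could be hidden. Where short gaps predominate, the reverse holds.

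**Working it through.** **1. The plan's own follow-up figure.** The synopsis gives a maximum of about 270 days of active participation, as three active periods of about 90 days: 3 × 90 = 270. This reproduces. It counts active periods only and excludes the inactive gaps, during which AEs are also collected.

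**2. Attribution windows.** For any dose followed by another, the window is the date of the next dose minus the date of this dose. For a subject's last dose it runs to the end of AE collection.

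| Dose | Shortest | Longest |
|---|---|---|
| Doses 1 and 2, pubertal/postpubertal, protocol collection | 3 days | none stated; gaps over 6 months planned for |
| Doses 1 and 2, if SAP 7.9.1 is read as a limit per dose | 3 days | 90 + 7 = 97 days |
| Dose 3, and the single prepubertal dose | planned end 90 − 7 = 83 days | 97 days |

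Even with the SAP 7.9.1 limit, the longest window is 97 / 3 ≈ 32 times the shortest. A pubertal/postpubertal subject who stays enrolled without another treated attack keeps adding events to the last dose received.

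**3. Would a later event be counted?** Take an AE reported at a monthly call on Day 200 after dose 1, with no second dose yet. Protocol 4.1.3.2 collects it. SAP 7.9.1 makes it treatment-emergent because it follows the first dose. SAP 10.2.11 assigns it to exposure 1. Neither derivation excludes it. By contrast, SAP 10.2.7 gives concomitant medication a 5-day window, and SAP 10.2.14 gives rescue medication 48+4 hours.

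**4. Illustration of size.** The documents give no background AE rate, so this is an assumption: constant risk, with 20% or 40% of subjects having an AE in 90 days. For one subject with a window of d days, P(at least one AE) = 1 − (1 − p)^(d/90).

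| Window d | p = 20% | p = 40% |
|---|---|---|
| 3 days | 1 − 0.8^(3/90) = 0.7% | 1 − 0.6^(3/90) = 1.7% |
| 90 days | 20% | 40% |
| 97 days | 1 − 0.8^(97/90) = 21% | 1 − 0.6^(97/90) = 42% |
| 180 days | 1 − 0.8² = 36% | 1 − 0.6² = 64% |

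The drug effect is nil throughout. These are probabilities for a subject with that window. A table column averages over mixed windows, and the documents do not give the distribution of gaps needed to compute that average.

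**5. Does a rate remove the problem?** Under the same model the event rate is −ln(1 − p)/90 per day, or 0.25 (p = 20%) and 0.57 (p = 40%) per 100 subject-days, for every window length.

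**The case against.** The strongest reply is that SAP 7.9.1 already ends collection at the Day 90 (±7) visit, and that Protocol 7.17.4.1 asks investigators to contact the sponsor about AEs after the observation period. A reader who sees only SAP 10.2.11 might infer that follow-up is unlimited for every dose. The documents do not support that: dose 3 and the prepubertal dose have a planned end near Day 97. But the SAP sentence describes collection. It is not written into the treatment-emergent definition or the attribution rule, and it conflicts with Protocol 7.16, 4.1.3.2 and Appendix 3. For doses 1 and 2 the objection does not remove the problem.

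A reader might also infer windows of more than a year. The protocol history (14 June 2011 to 18 March 2016, with the repeat-attack part still open) makes this possible but does not show that it occurred. The documents support only that no maximum is set and that gaps over 6 months are foreseen.

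Three further points stand and limit the weight of the concern:
- The tables are descriptive, and no test compares exposures. The all-TEAE summary does not depend on attribution to a dose, and the relatedness tables and the AE and dosing listings help a reader judge late events.
- Protocol 10.6 does not say that the safety assessment rests on frequency by exposure number; exposure number appears in a separate sentence on tabulation.
- HAE attacks and non-serious injection site reactions are not reported as AEs (Protocol 7.17.1.1), so the true background rate could lie outside the range assumed here.

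Finally, keeping every event attributed to some dose is the more inclusive choice in a small paediatric safety study. That argues for showing late events clearly, as the fix does. It does not justify percentages without a time base.

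**Conclusion.** The point holds in a bounded form. Followed literally, the SAP attributes AEs to doses 1 and 2 in pubertal/postpubertal subjects over anything from 3 days to an unstated maximum, while dose 3 and the prepubertal dose stop near Day 97. The by-exposure percentages, and the two pubertal-status columns for exposure 1, therefore reflect unequal follow-up that the outputs do not display. The SAP and protocol also disagree on when AE collection ends.

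The size for an individual subject is about 1% to 2% over 3 days against 36% to 64% over 180 days, resting on an assumed constant risk of 20% to 40% per 90 days. The effect on a column cannot be computed from the documents. It would be wrong to infer that observed differences between exposures must be due to follow-up; the finding is that the planned tables could not tell the two apart. The change should be made before the final tables are produced, but the overall TEAE summary is not undermined by the attribution rule.

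**What to change.** 1. **Main remedy.** In the by-exposure TEAE tables, add subject-days of follow-up and events per 100 subject-days for each exposure and each column.
2. **Common end.** Count events in those tables from dosing to the earlier of the next dose or Day 97, which is the SAP's own 90 + 7 days. Use the same end for the subject-days.
3. **Late events.** Show later events separately as beyond Day 97, and keep them in the overall TEAE table and the listings.
4. **Reconcile.** Align SAP 7.9.1 with Protocol 7.16, 4.1.3.2 and Appendix 3 on when AE collection ends.

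The cost is SAP wording, one derived variable and a denominator, all from dates already collected. The downside is that a few late AEs leave the by-exposure percentages. The cap alone is not enough: windows of 3 to 97 days remain, which on the illustration is still about 1% against 21%, or 2% against 42%. That is why the rates come first.
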